5.2.2 Baseline Procedures

There are no mandatory visit windows defined in this study, however it is recommended that baseline assessments should occur within 10 weeks prior to the index procedure; except for MSCT^v.

- Heart Team assessment for enrolled subjects who are <80 years of age and have a STS predicted risk of mortality of <8%. The Heart Team's assessment must be documented on the Heart Team Assessment form.
- Informed Consent (patient Informed Consent or Data Release Form)
- Demographics and Medical History
- Physical Examination
- NYHA functional classification
- Risk Scores^{vi}, including
 - Logistic EuroSCORE
 - EuroSCORE II
 - Society of Thoracic Surgeons Score for predicted risk of mortality
- Katz ADL score
- Trans-Thoracic Echocardiogram (TTE)
 - Please refer to the Appendix B for recommended TTE acquisition guidelines and images.
- MSCT (peripheral vasculature and aortic annulus)
 - Please refer to Appendix C for recommended MSCT acquisition guidelines.
- 12-lead Electrocardiogram (ECG)
- Relevant medications
- Modified Rankin Score (mRS)
- Review of relevant adverse events and device deficiencies (see section 5.7 for requirements)

5.2.3 Implant Procedure

The implantation procedure is performed according to the standard procedures of the implanting physicians. Procedural aspects specific to the Evolut R System should be performed according to the Instructions for Use (and/or IB for Australia).

Per VARC 2, up to 72 hours continuous rhythm monitoring is recommended in order to maximize detection of arrhythmias.

The following implant data will be collected and recorded on the implant e-CRF:

- Operative information
- Serial number, valve size and disposition of implanted valve or opened valve packages
- Documentation of device failure or malfunction (as applicable)
- Review of relevant adverse events and device deficiencies (see section 5.7 for requirements)

^v Pre-implant MSCT and TTE must be performed within 365 days of index procedure

^{vi} Definitions of EuroSCORE, STS, and other co-morbidities are provided in Appendix D

Attempted procedure

An attempted procedure is one where the trial subject has entered the procedure room for implantation, but did not receive an Evolut R TAV for any reason.

If a procedure was attempted, and the Evolut R TAV is not implanted, the subject will be followed for safety reporting for 30 days post-attempted implant, and then exited from the trial. AE data should be collected on the AE e-CRF, and trial exit data on the Trial Exit e-CRF.

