5.4.4 Subject Disposition

The Investigation site will maintain a log of all subjects enrolled in the clinical study, assigning an identification code linked to their names, alternative subject identification or contact information.

There are several scenarios in which a subject may exit the trial. Table 5 below details how the data will be handled for each scenario.

Table 5. Trial Exit Scenarios

Scenario	Follow-up Required	e-CRFs Required
Subject enrolled, but no implant attempted (i.e. not taken to the procedure room for implantation)	None	
 ▪ Inclusion/Exclusion e-CRF ▪ Baseline e-CRF (as applicable) ▪ AE e-CRF (as applicable) ▪ Trial Exit e-CRF
Subject enrolled, implant attempted (i.e. taken to the procedure room), but the subject does not receive the Evolut R TAV	30 days post-attempted implant for safety only	
 ▪ Inclusion/Exclusion e-CRF ▪ Baseline e-CRF (including TTE) ▪ Implant e-CRF ▪ Discharge e-CRF ▪ 30 Day e-CRF ▪ AE e-CRF (as applicable) ▪ Trial Exit e-CRF
Subject enrolled, implanted with Evolut R TAV, and has his/her valve explanted	Discharge following explant hospitalization or 30 days post implant (whichever comes later).	
 ▪ All required e-CRFs through last visit completed ▪ Surgical Reintervention e-CRF ▪ AE e-CRF (as applicable) ▪ Trial Exit e-CRF
Subject enrolled, implanted with Evolut R TAV, and exits the trial early due to any of the following: 
 ▪ Lost to Follow-up ▪ Death ▪ Withdrawal 	Through point of death, withdrawal, or last visit completed	
 ▪ All required e-CRFs through last visit completed ▪ AE e-CRF (as applicable) ▪ Trial Exit e-CRF
Subject enrolled, implanted and completes the trial requirements	Through 3 year follow-up	
 ▪ All required e-CRFs ▪ AE e-CRF (as appropriate) ▪ Trial Exit e-CRF

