3.4. Analysis Sets

Subjects who are taken to the procedure room for implantation will comprise the study population evaluated for the study objectives and associated endpoints.

The analysis sets are further defined as follows:

- **Safety Set (Attempted Implant):** The safety set includes all subjects who are brought into the procedure room for implantation.
- **Device Success/ Hemodynamic Performance Set (Implanted):** The device success/ hemodynamic performance set includes all subjects who are implanted with the Evolut R TAV, defined as the Evolut R TAV is placed in the aortic annulus and completely released from the EnVeo R catheter delivery system.

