3.5. Kaplan-Meier Analyses

In the Kaplan-Meier analysis, the product-limit estimate of the event rate, the number of subjects at risk, the number of subjects with events, the Peto standard error of the estimate, and the loglog transformed 95% confidence interval using the Peto standard error at 1 month (30 days), 1 year (365 days), 2 years (730 days) and 3 years (1095 days) will be presented.

For subjects without an event, the date of censoring will be the latest date of all follow-up visits, assessments, and events (including death in those objectives where death is not the endpoint).

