3.6.2. Primary Endpoint Definition

The primary endpoint is the binary rate of all-cause mortality at 30 days post procedure. The numerator will be the number of subjects who died on or before 30 days post procedure, and the denominator will be the number of subjects in the safety set (defined in section Analysis Sets 3.4) who died on or before 30 days post procedure, or whose latest date of all follow-up visits, assessments, and events is at least 30 days post procedure.

In addition, the KM event rates for all-cause mortality at 30 days, 1 year, 2 years and 3 years, as well as the KM plot will be provided.

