3.6.5. Data Collection and Analysis Methods

Death data will be collected on a separate site death case report form. All-cause death events will be adjudicated by the CEC. And the data on the CEC death adjudication form will be used in the analysis.

The all-cause mortality rate at 30 days post procedure will be compared with the performance goal of 10%, with a one-sided Fisher exact test at the 0.05 significance level. The analysis for this objective will be based on the safety set.

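### Protocol-driven exits censor failed attempts and explants from the 1-3 year safety-set mortality curve, so late rates may be slightly understated

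*Protocol*

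**What the plan says.** **Analysis set.** SAP 3.4 states: "The safety set includes all subjects who are brought into the procedure room for implantation". SAP 3.6.5 says of the mortality objective: "The analysis for this objective will be based on the safety set".

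**Late rates.** Within that objective, SAP 3.6.2 adds "the KM event rates for all-cause mortality at 30 days, 1 year, 2 years and 3 years". No other set is named for these curves.

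**Follow-up.** It depends on what happened to the valve (Protocol 5.2.3 and Table 5 in 5.4.4):

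- Attempted, not implanted: "the subject will be followed for safety reporting for 30 days post-attempted implant, and then exited from the trial". Table 5 agrees: "30 days post-attempted implant for safety only".
- Implanted, then explanted: "Discharge following explant hospitalization or 30 days post implant (whichever comes later".
- Implanted and completing: "Through 3 year follow-up".

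**Censoring.** SAP 3.5: "For subjects without an event, the date of censoring will be the latest date of all follow-up visits, assessments, and events". SAP 3.3 likewise censors drop-outs when they discontinue.

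**Sensitivity analyses.** The complete-case, best-case, worst-case and tipping-point analyses in SAP 3.6.6 concern the 30-day primary endpoint only.

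**The concern.** Kaplan-Meier estimation treats a censored subject as having the same later risk as those still under observation. Here two groups are censored by rule because of what happened to the device: it was not implanted, or it was removed. After day 30 the curve contains no information from failed attempts, and it loses each explanted subject at exit. It still carries the safety-set label, although by then it rests almost entirely on subjects who have the valve in place.

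What is at stake is the reading of the 1-, 2- and 3-year mortality rates. If exited subjects have higher later mortality, which is plausible, those rates are too low for the population named. Nothing in the SAP would show a reader how many subjects left this way or how far the rates could move.

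**Working it through.** **1. The plan's own figure.** The only relevant calculation in the documents is the sample size for the 30-day endpoint. Inputs (Protocol 2.7.3, SAP 3.6.4): performance goal 10.0%, expected rate 7.3%, one-sided alpha 0.05, power 90%. With an exact one-sample binomial test and n = 934, the null is rejected at 78 deaths or fewer. The type I error is 0.0493 and the power 0.901, so 934 is reproduced. Attempted subjects are followed to day 30, and explanted subjects at least that long, so neither this figure nor the primary test is touched.

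**2. Model for the late rates.** Let f be the share of the safety set that exits by protocol, s the 30-day survival (taken as equal in both groups), M the mortality of implanted subjects at the horizon, c = (1 - M)/s their survival beyond day 30, and h the hazard ratio after day 30 for exited versus implanted subjects.

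- Kaplan-Meier survival with exits censored at day 30: s × c
- Survival if everyone were followed: (1 - f) × s × c + f × s × c^h
- Understatement of mortality: f × s × (c - c^h)

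Only s = 1 - 0.073 = 0.927 comes from the documents (the expected rate). The rest is assumed: f = 1-3%, h = 0.75-3, and M = 15% for an earlier and 35% for a later horizon. All exits are placed at day 30, which is too early for later explants and so tends to overstate the effect.

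**3. Worked case.** For M = 35%, c = 0.65/0.927 = 0.7012. With f = 3% and h = 3, c^h = 0.3447, and 0.03 × 0.927 × (0.7012 - 0.3447) = 0.0099, or 0.99 points.

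**4. Range.** Understatement in percentage points; a minus sign means the rate is overstated.

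| h | M = 15%, f = 1% to 3% | M = 35%, f = 1% to 3% |
|---|---|---|
| 0.75 | -0.02 to -0.06 | -0.06 to -0.18 |
| 1 | 0 | 0 |
| 1.5 | 0.04 to 0.11 | 0.11 to 0.32 |
| 2 | 0.07 to 0.21 | 0.19 to 0.58 |
| 3 | 0.14 to 0.41 | 0.33 to 0.99 |

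Sampling standard error at n = 1000, √(M(1 - M)/n): 1.13 points at 15% and 1.51 points at 35%. More extreme inputs (f = 5%, h = 5) give 1.25 and 2.46 points.

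**5. Observed early deaths reduce the effect.** A cruder calculation sets the Kaplan-Meier rate equal to M and gives exited subjects k times that mortality, so the shortfall is f × M × (k - 1). With f = 3%, M = 30% and k = 2 this is 0.9 points. But deaths of exited subjects up to day 30 are counted. If their 30-day mortality is also doubled, to 14.6%:

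- 30-day survival of the set: 0.97 × 0.927 + 0.03 × 0.854 = 0.9248
- Kaplan-Meier mortality: 1 - 0.9248 × (0.70/0.927) = 30.17%
- Mortality with full follow-up: 0.97 × 30% + 0.03 × 60% = 30.9%

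The shortfall is 0.73 points, against a standard error of 1.45.

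**6. Bounds without a hazard assumption.** At f = 2%, if every exited subject dies, the understatement is 0.02 × (1 - M): 1.70 points at M = 15% and 1.30 at M = 35%. If none dies after day 30, the rate is overstated by 0.02 × (0.927 - (1 - M)): 0.15 and 0.55 points.

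**The case against.** The strongest reply is that this concerns a descriptive extra. The protocol's mortality endpoint and all its secondary safety endpoints stop at 30 days, the only 1-year endpoint is hemodynamic, and SAP 3.6.2 attaches no hypothesis to the later rates. The SAP also reports numbers at risk at each time point and the number of subjects in each analysis, and the protocol records vital status at exit. All of this is correct and limits the importance of the point. It does not remove it: numbers at risk do not separate protocol exits from other censoring, and vital status at exit says nothing about what follows.

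Some stronger readings are tempting but not supported:

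- *Explanted subjects leave at about 30 days.* Table 5 takes the later of two dates. A subject explanted at month 20 contributes 20 months, and a death during the explant stay is captured.
- *Late mortality is understated in the device's favour.* The documents contain no non-implant rate, explant rate or mortality after exit. An attempted procedure covers non-receipt of the valve for any reason, not only device failure. The bias is zero at equal hazard and reverses below it.
- *Table 5 contradicts Protocol 2.5.* The three-year follow-up of implanted subjects stated there is a premise for estimating study duration. Table 5 lists exceptions to it: explant, death, withdrawal, loss to follow-up.
- *Moving the late curve to the implanted set solves the problem.* That drops the observed early deaths of failed attempts and leaves the censoring at explant in place. In the example of step 5 it lowers the reported rate from 30.17% to 30.0%, further from 30.9%.

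**Conclusion.** The mismatch between the safety set and the follow-up rules is real and follows directly from the two documents. Its consequence is conditional: the 1-3 year rates may be understated if subjects who exit have higher later mortality. With 1-3% exiting and 1.5 to 3 times the later hazard, the shortfall is from under 0.1 to about 1 percentage point, below one standard error. These shares, hazard ratios and late mortality levels are assumptions. The worst-case bound can exceed one standard error (1.70 points against 1.13 at f = 2% and M = 15%), which is a reason to report the bounds. The primary endpoint, its test and the sample size stand. This is a low-cost improvement to a descriptive result and not a flaw that threatens the study's conclusion.

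**What to change.** 1. **Protocol Table 5 and 5.2.3.** Keep explanted subjects, and preferably attempted-but-not-implanted subjects, in vital-status-only follow-up to 3 years by telephone or records. No clinic visit is added. Protocol 5.2.5 already accepts telephone contact, and 5.4.3 already expects the implanting center to go on following such subjects in routine care.
2. **SAP 3.5.** State that these subjects are censored in the mortality analysis only when vital status is unknown, at the date they were last known to be alive.
3. **If vital status is not collected for the attempted group, SAP 3.6.2.** Keep 30-day mortality in the safety set, present and label the 1-, 2- and 3-year curve as the implanted set, and report the number of subjects censored by protocol exit with best- and worst-case bounds. This is a fallback. It does not replace item 1 for explanted subjects.

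Cost: a table amendment, a few SAP sentences, and a yearly vital-status check on what is likely a small number of subjects. The synopsis describes implanted subjects as consented for three years of follow-up. For the attempted group, the sponsor should confirm that the consent wording covers contact after day 30.

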5.2.4 Discharge

Prior to hospital discharge, the following data will be collected.

- 12-lead ECG
- Modified Rankin Score (mRS)
- Physical Examination
- Trans-Thoracic Echocardiogram (for device success)
 - Per the VARC 2 definition for Device Success, the recommended time window for the TTE is 24 hours to 7 days Post Procedure;
 - Please refer to the Appendix B for recommended TTE acquisition guidelines and images.
- Relevant medication use.
- Review of relevant adverse events and device deficiencies (see section 5.7 for requirements)

5.2.5 Follow-up Visits

Patients are followed per standard of care. Information from visits performed at the implanting hospital should preferably be used for the follow-up visits. If the patient did not return to the implanting hospital, but was followed at a local hospital, this information can be used as an alternative. If no hospital visit occurred, a telephone follow-up visit can be performed.

5.2.6 30 days

There are no mandatory visit windows defined in this study; however it is recommended that the 30-day follow up visit should occur between 30 and 60 days post procedure.

- NYHA functional classification
- 12-lead ECG
- Physical Examination
- Relevant medication use.
- Modified Rankin Score (mRS)
- Review of relevant adverse events and device deficiencies (see section 5.7 for requirements)

5.2.7 One Year

There are no mandatory visit windows defined in this study; however it is recommended that the 1-year follow up visit should occur between 365 and 425 days post procedure.

- NYHA functional classification
- Trans-Thoracic Echocardiogram (TTE)
 - Please refer to the Appendix B for detailed instructions, guidelines and required images.
- 12-lead ECG

- Physical Examination
- Relevant medication use.
- Modified Rankin Score (mRS)
- Review of relevant adverse events and device deficiencies (see section 5.7 for requirements)

5.2.8 Two Years

There are no mandatory visit windows defined in this study; however it is recommended that the 2-year follow up visit should occur between 730 and 790 days post procedure.

- NYHA functional classification
- 12-lead ECG
- Physical Examination
- Relevant medication use.
- Modified Rankin Score (mRS)
- Review of relevant adverse events and device deficiencies (see section 5.7 for requirements)

5.2.9 Three Years

There are no mandatory visit windows defined in this study; however it is recommended that the 3-year follow up visit should occur between 1095 and 1155 days post procedure.

- NYHA functional classification
- 12-lead ECG
- Physical Examination
- Relevant medication use.
- Modified Rankin Score (mRS)
- Review of relevant adverse events and device deficiencies (see section 5.7 for requirements)

5.2.10 Four and Five Years

If, based on clinical assessments during the course of the study, follow up is extended to up to 5 years post procedure, the follow up visits are recommended to occur between 1460 and 1520 days for the 4-year follow up visit and between 1825 and 1885 days for the 5-year follow up visit.

- NYHA functional classification
- 12-lead ECG
- Physical Examination
- Relevant medication use.
- Modified Rankin Score (mRS)
- Review of relevant adverse events and device deficiencies (see section 5.7 for requirements)

5.2.11 Other Evaluations

- A mRS assessment should be performed at baseline, all scheduled visits and at 90 days after the onset of any stroke.

5.3 Trial Assessments

5.3.1 Relevant Medications

Use of the following medications will be collected at baseline and at each postoperative interval and recorded on the appropriate e-CRF:

- Anticoagulants
- Antiplatelets
- Aspirin (including Carbasalate calcium)

The Investigator's standard clinical practice will determine the appropriate anti-thrombotic medication use for each subject.

5.3.2 Risk Scores

The Logistic EuroSCORE, EuroSCORE II and Society of Thoracic Surgeons' (STS) risk models predict the risk of operative mortality after adult cardiac surgery on the basis of patient demographic and clinical variables.

The risk scores should be calculated at baseline for each subject using the online calculator:

- Logistic EuroSCORE: <http://euroscore.org/calcold.html>
- EuroSCORE II: <http://euroscore.org/calc.html>
- STS Risk Score: <http://riskcalc.sts.org/stswebriskcalc/#/>

The online calculator provides additional guidance and definitions for each of the parameters used to calculate the scores. The predicted risks of mortality should be recorded on the Baseline e-CRF. The Risk Scores should be printed from the online calculators and filed as source documentation for trial subjects.

5.3.3 Heart Team Assessment

Patients with age <80 years and a STS predicted risk of mortality of <8% must be evaluated by a heart team to confirm the patient is at high or greater risk for AVR due to frailty or comorbidities.

The Heart Team's assessment must be documented on the Heart Team Assessment form and signed by the PI or delegated Investigator(s) (as documented on the Delegated Task List) (see section 4.5.2).

5.3.4 Katz ADL

Katz Index of Independence in Activities of Daily Living: the Katz Index of Independence in Activities of Daily Living, in short, the Katz ADL, is a questionnaire to assess functional status as a measurement of the patient's ability to perform activities of daily living independently. The index ranks adequacy of performance in six functions. Patients are scored yes or no for independence in each of the six functions. A score of six indicates full function and 2 or less indicates severe functional impairment.

Detailed information about the Katz ADL including guidelines to perform them can be found in the Investigator Site File. The site will record frailty assessment data on the appropriate e-CRF.

5.3.5 Multi-slice Computed Tomography

All subjects enrolled in this study must have a routine cardiac Multi-slice Computed Tomography (MSCT) recording available at baseline for evaluation of the aortic valve anatomy, determination of aortic root dimensions for device sizing, and for evaluation of peripheral vessel dimensions and anatomy.

MSCT's are performed per standard care in all investigational sites (see section 4.1.2.). Please refer to Appendix C for recommended MSCT acquisition guidelines. If no recent^{vii} MSCT image is available or planned per standard care, the patient should **not** be enrolled in this study (see section 5.1).

Data to be recorded from the MSCT recording on the appropriate e-CRF include the following:

- Aortic valve annulus perimeter
- Mean Sinus of Valsalva diameter
- Mean Sinus of Valsalva height
- Calcification of Aorta and LVOT
- Access vessel tortuosity and calcification

5.3.6 Echocardiography

Transthoracic echocardiography (TTE) exams, performed per standard care, are collected at the following intervals: baseline (pre-implant), 24 hours to 7 days (for device success) and 1 year.

These TTE exams will be sent to the Echo Core Lab for central assessment. Please refer to Appendix B for recommended TTE acquisition guidelines and images.

Sites should make every effort to utilize the same echo machine for all patients at the above mentioned intervals. Additionally, sites should perform regular maintenance and calibration of echo machines per local standards and ensure proper documentation is available for audit, as applicable.

5.3.7 12-Lead ECG

The standard 12-lead ECG will be utilized as a diagnostic and prognostic tool. All ECGs are analyzed utilizing both qualitative and quantitative methodology, to assess cardiac rhythm, noting any cardiac arrhythmias and indications for pacing. The site will record ECG data on the appropriate e-CRF.

5.3.8 NYHA Functional Classification

The New York Heart Association (NYHA) Functional Classification is a system for defining cardiac disease and related functional limitations into four broad categorizations as defined in Table 4.

^{vii} Pre-implant MSCT must be performed within 365 days of index procedure

Table 4. New York Heart Association (NYHA) Functional Classification

Classification	Description
Class I	Subject with cardiac disease but without resulting limitations of physical activity. Ordinary physical activity does not cause undue fatigue, palpitation, dyspnea, or anginal pain.
Class II	Subjects with cardiac disease resulting in slight limitation of physical activity. They are comfortable at rest. Ordinary physical activity results in fatigue, palpitation, dyspnea, or anginal pain.
Class III	Subjects with cardiac disease resulting in marked limitation of physical activity. They are comfortable at rest. Less than ordinary physical activity causes fatigue, palpitation, dyspnea, or anginal pain.
Class IV	Subjects with cardiac disease resulting in inability to carry on any physical activity without discomfort. Symptoms of cardiac insufficiency or of the anginal syndrome may be present even at rest. If any physical activity is undertaken, discomfort is increased.

NYHA classification will be assessed at baseline, 30 days, 1, 2 and 3 years, and the results recorded on the appropriate e-CRF.

